1. STUDY OBJECTIVES

1.1 **Primary Study Aims:** Determine the feasibility of an integrated psychosocial treatment (ACT + MBRP) in veterans with chronic pain with evidence of opioid-related problems. Chronic pain patients ($n = 120$) who are receiving opioid therapy and who are identified as opioid misusing, abusing, or dependent will be recruited from the Albuquerque Veterans Administration (VA) Hospital. Participants will be randomized to receive standard care or standard care in addition to ACT+MBRP. **Hypothesis 1: Feasibility of recruitment:** Given the high prevalence of both chronic pain and opioid-related problems in VA populations, we hypothesize it will be possible to recruit our target sample size ($n = 120$) within a 15-18 month timeframe. **Hypothesis 2: Feasibility of retention:** Drop-out rates will be consistent with other trials of similar psychosocial interventions for chronic pain (i.e., < 20%^{5,21-23}).

1.2 **Secondary Study Aims:** To examine weekly progress on specific therapy targets (e.g., pain acceptance, self-compassion, opioid craving) in the interventions in order to identify potential mechanisms of change and to identify the choice of intermediate endpoints for a larger randomized clinical trial.

Hypothesis 1: Evidence of treatment mechanisms: The combined ACT+MBRP treatments will be associated with changes in treatment mechanisms specified within the therapeutic models and in a manner consistent with that of previous work on ACT and MBRP, in comparison with standard care.

Hypothesis 2: Selection of intermediate endpoints: Weekly progress measures will provide data indicating measures of treatment-specific mechanisms that are most sensitive to change. We hypothesize that acceptance of pain discomfort will be most sensitive to change in ACT and that reductions in reactivity to substance craving will be most sensitive to change in MBRP.

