6. STUDY PROCEDURES

6.1 Schedule of Evaluations

Assessment	Telephone Screening: (Day-30 to Day -1)	Baseline, Enrollment, Randomization Visit 1 (Day 0)	Treatment Visit Visit 2-12 (W2-12)	Final Treatment Visit 13 (W13)	6 mo. follow-up Visit 14 (W37)
Screening	X				
Informed Consent Form	X	X			
Demographics		X			
Pain-Related Information		X			X
Clinical Outcomes		X		X	X
Weekly Assessments		X	X	X	X

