- Current Opioid Misuse Measure (COMM) - We will also collect information on current opioid misuse using the COMM, a measure of aberrant opioid-related behaviors over the past month³. The recommended cut-score of 12 has adequate sensitivity (77%) and specificity (77%) for a current diagnosis of prescription drug abuse³.
- Structured Clinical Interview for DSM-IV (SCID) – The Substance Abuse and Dependence module of the SCID will be conducted with all participants.

Clinical Outcomes:

- Pain Behavior - *PROMIS Bank v1.0 Pain Behavior*
- Pain Interference - *PROMIS Bank v1.0 Pain Interference*
- Disability – *Sickness Impact Profile* (SIP) – The SIP is a measure of health-related disability⁴. It has demonstrated utility in chronic pain settings and provides a detailed assessment of

functioning across multiple domains. The SIP has been widely used in chronic pain settings and has demonstrated sensitivity to intervention^{5,59,60}.

- Pain intensity, including current and least/most/usual over the past week, will be assessed via a 0 (no pain) -10 (maximum possible pain) numerical rating scale (NRS). Assessing pain intensity via NRS is a widely-used and well-established method in studies of pain^{61,62}.

Randomization

Randomization will occur following baseline assessment. We will use a random order variable-sized block randomization procedure with block sizes of 2, 4, and 6. The investigators will be blind to the size of each block and randomization allocation.

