Analyses to Test Secondary Aim Hypotheses. The primary goal of Aim 2 is to identify potential mechanisms of change and intermediate endpoints for future randomized clinical trials comparing ACT+MBRP to standard care. We will accomplish this goal by examining initial level and changes in targeted mechanisms over time during the course of treatment, as well as the association between changes in targeted mechanisms during treatment and 6-month follow-up measures of clinical outcomes. Targeted mechanisms will include (1) pain acceptance (2) psychological flexibility, (3) experiential avoidance, (4) opioid craving, and (5) reactivity to pain and craving, and will be examined using latent growth curve models with fixed effects of treatment and random effects of time. These analyses will provide an estimate of the initial level of each targeted mechanism (i.e., intercept) and the change in the targeted mechanisms over time (slope). Clinical outcome measures will include pain interference, pain behavior, and opioid misuse and will be examined using mediation analyses within the context of latent growth curve modeling⁶⁴, as we have done in prior studies^{63,65}. Specifically, as shown in simplified form in Figure 2, we will examine whether initial level (intercept) or changes (slope) in the targeted mechanisms ("M" in figure 2) during treatment mediate the effect of treatment on 6-month clinical outcomes, controlling for baseline levels of the outcomes. These analyses will also provide a test of Aim 2 Hypothesis 2, which is to identify those measures that are most sensitive to change (measures with the largest slope). Identifying measures that are more sensitive to change will help us in identifying intermediate endpoints for a larger RCT. Validation of intermediate endpoints is challenging and it is often recommended that meta-analytic methods be used⁶⁶, but alternative methods have been developed that allow for the evaluation of endpoints in mental-health clinical trials⁶⁷.

Figure 2. Simplified mediation model (excludes residual terms and covariances)

models will be estimated using the product of coefficients method⁶⁸, which provides an estimate of the mediated effect by multiplying regression coefficients for the regression of the mediators (e.g., slope of targeted mechanism) on treatment condition (i.e., a-path or α) and for the regression of the clinical

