outcome on the mediators (i.e., b-path or β). We will use bootstrapping to obtain 95% confidence intervals of the mediated effect⁶⁹. We will use maximum likelihood estimation for all analyses, which provides the variance-covariance matrix for all available data and is the preferred method for estimation when some data are missing⁷⁰. Attrition analyses will determine whether there are any differences in study variables between those with missing and complete data. Study variables associated with missing data will be covaried in all analyses.

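### Section 9.1 tests each mechanism's initial level as a mediator, but with time zero at the pre-randomisation Day 0 visit treatment cannot act through that level, so it belongs in the model as a covariate

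*Combined protocol and SAP*

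**What the plan says.** Section 9.1, on the secondary aim, fixes the ingredients of the mediation analysis:

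- Mediators: "Targeted mechanisms will include (1) pain acceptance (2) psychological flexibility, (3) experiential avoidance, (4) opioid craving, and (5) reactivity to pain and craving".
- Outcomes: "Clinical outcome measures will include pain interference, pain behavior, and opioid misuse", taken at 6 months with their baseline values controlled.
- Growth factors: "we will examine whether initial level (intercept) or changes (slope) in the targeted mechanisms" mediate the treatment effect.
- Test: a product method "which provides an estimate of the mediated effect by multiplying regression coefficients", the first being the regression of the mediator on treatment (a-path) and the second the regression of the outcome on the mediator (b-path).
- Inference: "We will use bootstrapping to obtain 95% confidence intervals of the mediated effect".

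On timing, Section 6.2.2 says "Randomization will occur following baseline assessment", and Section 4.3 has randomisation directly after consent and assessment. The schedule in Section 6.1 ticks the weekly assessments in the column headed "Baseline, Enrollment, Randomization Visit 1 (Day 0").

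Other places read differently. The opening synopsis describes the weekly data as gathered over the 12 treatment weeks. The baseline battery in Section 6.2.2 does not list the pain-acceptance, self-compassion or craving questionnaires. Section 6.2.4 lists them under follow-up visits. The payment log in Appendix VI labels the first paid weekly assessment as week 1 of ACT.

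The documents do not state the growth model's time origin, any multiplicity control, or any order among the mediation tests.

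**The concern.** A variable mediates a treatment effect only if treatment moves it. A level measured before allocation cannot be moved by allocation, so a significant product through such a level carries no information about mechanism. It reflects the luck of the allocation on a variable that predicts the outcome.

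Section 9.1 also treats the same event in two ways. Its preliminary analyses regard a significant baseline difference between arms as something to adjust for. The mediation analysis would let a baseline difference in a mechanism count as evidence of how treatment works.

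What is at stake is the list of potential mechanisms that the pilot hands to a larger trial. An intercept mediator on that list would be read as a finding about ACT+MBRP.

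**Working it through.** **1. The plan's own figures.** The plan gives neither a number of mediation tests nor an error rate for them, so there is nothing to reproduce on this point itself. Its one fully specified figure is 60 per condition in Section 9.2 (d = 0.25, two-sided 0.05, three assessments, correlation 0.43). It reproduces as a group-by-time interaction: f = 0.25/2 = 0.125, noncentrality 0.125² × 120 × 3 / (1 − 0.43) = 9.87, df 2 and 236, power 0.805. The size of 120 is used below.

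**2. The a-path under the schedule.** With time zero at Day 0, a = E(intercept | ACT+MBRP) − E(intercept | standard care) = 0, because both arms are random samples of the same pre-allocation distribution. The mediated effect is a × b = 0 × b = 0 for every b.

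**3. Number of tests.** Five mechanisms × 3 outcomes × 2 growth factors = 30, of which 5 × 3 = 15 use the intercept. This is an upper bound, since Section 9.1 does not say that every pair is modelled separately.

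**4. Error of one intercept test.** Simulation with 120 participants, true a = 0, percentile bootstrap 95% interval, 1,500 trials of 500 resamples, and the initial level treated as directly observed. The b values 0.43 and 0.71 are the sizes of the b-paths quoted in Section 9.2; 0 and 0.3 are assumptions.

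| b | share of trials with interval excluding 0 |
|---|---|
| 0 | 0.3% |
| 0.3 | 4.1% |
| 0.43 | 5.7% |
| 0.71 | 5.5% |

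Every one of these rejections is false.

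**5. Error over the 15 intercept tests.** The three outcomes for one mechanism share the same a-path, so there are only five independent chances at most. Ceiling: 1 − 0.95⁵ = 0.226. In simulation (4,000 trials per setting, both paths required to be significant, correlation among mechanisms 0, 0.3 or 0.6, b of 0.3, 0.6 or 1.0), the chance of at least one spurious intercept mediator ran from 0.11 to 0.21. The expected number ran from 0.19 to 0.75. If only three mechanisms could be measured weekly (an assumption), the count would be 3 × 3 × 2 = 18, with 9 on the intercept and a ceiling of 1 − 0.95³ = 0.143.

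**6. If the fitted intercept is not a clean Day 0 level.** Take an illustrative treatment effect of 0.5 SD over 12 weeks and fit a straight line. The difference between arms in the fitted intercept is then:

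| true course | time zero at baseline | time zero one week later |
|---|---|---|
| linear | 0.00 SD | −0.04 SD (0.5 × 1/12) |
| change only after week 9 | +0.10 SD | +0.10 SD |
| plateau by week 8 | −0.06 SD | −0.12 SD |

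The non-zero values in the baseline column are curvature forced into the intercept. They have no reading as a mechanism.

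**The case against.** The strongest reply is that the time origin is never given, and much of the text points away from Day 0: the synopsis, the baseline list in Section 6.2.2, Section 6.2.4 and Appendix VI. Section 9.1 itself speaks of level and change over the course of treatment. If the first point is a treatment visit, the intercept falls after randomisation and could in principle differ by arm. This stands, and it makes the conclusion conditional.

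It does not rescue the test. ACT begins in week 2, which is also the first weekly visit after baseline in Section 6.1. The craving scale and the diary ask about the past week, so at the first session they describe time that is mostly or wholly before treatment. The differences in step 6 that arise from curvature are misfit.

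It is also fair to say that the aim is secondary, that it seeks only potential mechanisms in a feasibility pilot, and that formal multiplicity control there is largely a matter of preference. That stands too. Removing a test that has nothing to detect is a separate matter from adjusting for multiplicity.

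**Conclusion.** The concern holds in a conditional form. With time zero at Day 0, as the Section 6.1 schedule implies, intercept mediation is zero by design. Each such test errs in about 4-6% of trials when b is non-zero. The chance of at least one spurious intercept mediator is about 11-21%, and at most about 23%. These family figures assume that five mechanisms and three outcomes are all tested, with 120 participants analysed and 5% per test. The last column of step 6 and the first-session argument above suggest that another origin would give the test little interpretable content.

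A reader might infer more than the documents support:

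- *That half the tests can only be false positives, whatever the coding.* This needs the Day 0 origin, which the plan does not state.
- *That the error is 1 − 0.95¹⁵ = 54% for the intercept tests, or 1 − 0.95³⁰ = 79% for all.* Both assume independent tests, which the shared a-paths rule out. The second also assumes that no slope mediates anything.
- *That spurious intercept mediators would become the next trial's intermediate endpoints.* Section 9.1 judges sensitivity to change by the largest slope, so an intercept does not enter that rule.
- *That Hypothesis 2 already sets pain acceptance and craving as primary mediators.* It says "acceptance of pain discomfort will be most sensitive to change in ACT", and for MBRP it names reactivity to craving, which Section 9.1 lists separately from craving. It concerns sensitivity to change, not mediation.

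**What to change.** - State in Section 9.1 that time zero is the Day 0 assessment. Reconcile the Section 6.1 schedule with the synopsis and with the baseline list in Section 6.2.2, so that all show the weekly questionnaires at baseline.
- Remove the intercept as a mediator. Use each mechanism's baseline level as a covariate; in the growth model this means fixing the path from treatment to the intercept at zero and letting the intercept predict the slope and the outcome.
- Test mediation through the slope only, and report those results as exploratory estimates with intervals.
- Optionally, name two primary mediator-outcome pairs. If this is done, the mediators should follow Hypothesis 2 as written: pain acceptance and reactivity to craving.

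The cost is wording. The schedule already calls for the Day 0 measures, so it needs no further participants or visits, and the mediation tests fall from up to 30 to up to 15.

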Demographic Information (Pre-treatment, Post-treatment, and 6 month follow-up assessment): Patient demographics (e.g., gender, age, educational achievement) and pain-related information (e.g., duration, location, history of treatment) will be collected during the pre-treatment assessment. We will re-assess pain-related information and treatment history at post-treatment and the 6-month follow-up assessment.

Clinical Outcome Measures (Pre-treatment, Post-treatment, and 6 month follow-up assessment): Given the relevance of interference from pain on key aspects of functioning in those with chronic pain, we will utilize the NIH PROMIS toolkit measures for pain behavior¹ and pain interference². Both PROMIS measures have evidence of excellent psychometric properties in chronic pain. We will also collect information on current opioid misuse using the Current Opioid Misuse Measure, a measure of aberrant opioid-related behaviors over the past month³. The recommended cut-score of 12 has adequate sensitivity (77%) and specificity (77%) for a current diagnosis of prescription drug abuse³. Finally, current pain intensity, as well as least, most, and average over the past seven days, will be assessed via 0-10 numerical ratings scales and disability will be assessed via the Sickness Impact Profile⁴.

Weekly Self-Report Progress Measures (20 minutes per week): In order to examine our secondary objective concerning mechanisms of change during treatment, we will collect weekly data during the 12 weeks of treatment to assess for change in specific therapy targets that are hypothesized to change during treatment. These weekly progress measures will include three self-report questionnaires, each of which has evidence for mediating treatment outcomes in either ACT for chronic pain⁵ or MBRP for substance use disorder^{6,7}. These measures include:

1. **Chronic Pain Acceptance Questionnaire (CPAQ⁸)**. The CPAQ is a 20-item measure of acceptance and willingness to have chronic pain. It is perhaps the most widely used measure of pain acceptance in

the literature and its psychometric properties, factor structure, and sensitivity to treatment are well established^{9,10}.

2. *Self-Compassion Scale (SCS)*¹¹. The SCS is a 26-item questionnaire which evaluates numerous aspects of mindfulness and self-compassion. Initial psychometric evaluations of the measure have provided support for its reliability and validity¹¹.

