9.2 Sample Size and Randomization

Commented [KV4]: Blocking

Statistical Power for Secondary Aims: We estimated statistical power for the mediation analyses using parameter estimates from prior studies of mediation following ACT for chronic pain⁵ and following MBRP for substance use disorders^{7,63} to estimate the effect sizes for the behavioral measures in the current study. Following ACT, numerous behavioral measures significantly mediated changes in disability, depression, pain-related anxiety, medical visits, and number of classes of prescribed analgesics, with large mediation effect sizes. The prior studies of MBRP have found that experiential avoidance, awareness, and nonjudgment significantly mediated the association between treatment and changes in craving ($\alpha = 0.56$; $\beta = -0.43$) and that craving significantly mediated the association between treatment and changes in substance use ($\alpha = -0.20$; $\beta = 0.71$). Based on these effect sizes and power estimates for testing mediation derived from a simulation study⁷¹, we will have power greater than 0.80 to detect significant mediating effects with the proposed sample size of 120.

Examining mechanisms of change assumes that treatment influences change in the clinical outcome measures at follow-up, thus we also estimated the power to detect a main effect of treatment on the clinical outcome measures. Effect size estimates were drawn from prior studies of ACT for patients with chronic pain^{5,23,60,72} and MBRP for substance use disorders^{52,63,73}. The effect sizes for ACT in comparison to treatment as usual or active treatment for chronic pain have ranged from 0.29 to 1.09. The effect sizes for MBRP in comparison to treatment as usual for substance use and craving have ranged from 0.21 to 0.52. Based on these studies, we estimate a minimum average effect size of $d=0.25$. Using a mixed-effects linear model with $\alpha=0.05$ (two-tailed test), three repeated assessments (baseline, end of treatment, 6-month follow-up), and a correlation among repeated measures of 0.43 (based on prior studies) we will need 60 subjects per condition (total $n = 120$) for 80% power to detect a main effect of ACT+MBRP in comparison to standard care.

Treatment Assignment Procedures

We will use a random order variable-sized block randomization procedure with block sizes of 2, 4, and 6. The investigators will be blind to the size of each block and randomization allocation.

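### Section 9.2 powers a three-assessment model of the treatment effect that section 9.1 never specifies, and Week 13 clinical outcomes are left with no proper role when Week 37 is missing (Aim 2)

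*Combined protocol and SAP*

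**What the plan says.** **Collection.** The synopsis schedules "Clinical Outcome Measures (Pre-treatment, Post-treatment, and 6 month follow-up assessment"), and the schedule in section 6.1 marks clinical outcomes at the baseline, Week 13 and Week 37 visits.

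**Sample size.** Section 9.2 justifies 60 per condition by a mixed-effects model with two-sided alpha 0.05, an effect size of 0.25, "three repeated assessments (baseline, end of treatment, 6-month follow-up") and "a correlation among repeated measures of 0.43 (based on prior studies"), giving 120 in all "for 80% power to detect a main effect of ACT+MBRP in comparison to standard care". It presents this as support for the mechanism work, since mediation presupposes a treatment effect on the clinical outcomes at follow-up.

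**Analysis.** The only analysis of clinical outcomes described in section 9.1 is the latent growth mediation model. It asks whether level or change in the mechanisms would "mediate the effect of treatment on 6-month clinical outcomes, controlling for baseline levels of the outcomes". Week 13 clinical outcomes are not mentioned.

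**Missing data.** Section 9.1 plans maximum likelihood, "which provides the variance-covariance matrix for all available data", then attrition analyses, and then the addition of study variables related to missingness as covariates in every analysis.

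**The concern.** The model that is powered and the model that is specified differ. One uses three assessments. The other uses the 6-month value adjusted for baseline.

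This matters for missing data. Maximum likelihood draws only on variables that are in the model. A participant who attends Week 13 and misses Week 37, 24 weeks later, has clinical scores on file that the specified model cannot use. If those scores predict who returns, and do so differently by arm, the Week 37 treatment effect can be distorted although the data that would correct it are in hand.

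The one stated rule that might bring Week 13 scores in, the covariate rule, would do so in a harmful way, because they are measured after treatment and carry part of its effect.

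Aim 2 is meant to guide a larger trial, so an error in the treatment effect would be carried forward.

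**Working it through.** **Inputs from the plan:** d = 0.25, ρ = 0.43, three assessments, two-sided alpha 0.05, 80% power, 60 per arm (all section 9.2); expected drop-out below 20% (section 1.1).

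**Assumptions, not in the documents:** equal correlation between all pairs of visits, SD 1, an effect of 0.25 at both post-baseline visits, and the drop-out and mediator settings stated below.

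**1. The plan's own figure.** N = 120 reproduces as a group-by-time F test. With f = 0.25/2 = 0.125, the noncentrality is f²·N·3/(1−ρ) = 0.015625 × 360/0.57 = 9.87 on 2 and 236 df, and power is 0.805. Read instead as a main effect on the mean of three assessments, the variance factor is (1 + 2 × 0.43)/3 = 0.62. That needs 156 per arm, and power at 60 per arm is 0.41.

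**2. Power of the comparison that 9.1 describes.** For the 6-month value adjusted for baseline, the variance factor is 1 − 0.43² = 0.8151.
- SE at 60 per arm = √(2 × 0.8151/60) = 0.165, and 0.25/0.165 = 1.52. Power = Φ(1.52 − 1.96) = 0.33.
- At 48 per arm (20% lost), power is 0.27.
- 80% power needs 2 × (1.96 + 0.84)² × 0.8151/0.25² ≈ 205 per arm.
- The mean of both post-baseline values, adjusted for baseline, has factor (1 + 0.43)/2 − 0.43² = 0.5301 and power 0.47 at 60 per arm.

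**3. The covariate rule applied to a Week 13 outcome.** Given baseline, the coefficient of Week 13 is ρ/(1+ρ) = 0.43/1.43 = 0.301. The treatment coefficient becomes 0.25 − 0.301 × 0.25 = 0.175. This happens even when loss is random. Simulation gives 0.173 to 0.179 across scenarios.

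**4. Bias without Week 13 in the model.** Suppose selection shifts the Week 13 mean of those who return by δ in one arm only. The Week 37 mean then shifts by ρδ, and baseline adjustment takes back ρ²δ. To first order this leaves ρ(1−ρ)δ = 0.245δ. If the worst fifth of one arm is lost outright, δ = φ(0.84)/0.8 = 0.280/0.8 = 0.35, so the estimate is 0.25 + 0.245 × 0.35 = 0.336.

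Large-sample simulation, true Week 37 effect 0.25. Loss is given as ACT+MBRP/standard care. OR is the odds ratio for loss per SD worse at Week 13. The mediator has a 0.5 SD treatment effect, no correlation with baseline, and correlation 0.3 with both later outcomes.

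| Loss after Week 13 | Baseline + Week 37 | Mediator also in likelihood | Week 13 modelled jointly |
|---|---|---|---|
| Random, 20%/20% | 0.25 | 0.25 | 0.25 |
| Same mechanism, OR 2.7, 20%/20% | 0.25 | 0.25 | 0.25 |
| ACT+MBRP only, OR 1.65, 20%/20% | 0.28 | 0.27 | 0.25 |
| ACT+MBRP only, OR 2.7, 20%/20% | 0.29 | 0.28 | 0.25 |
| Same mechanism, OR 2.7, 30%/10% | 0.29 | 0.28 | 0.25 |
| ACT+MBRP only, OR 2.7, 30%/10% | 0.31 | 0.29 | 0.25 |
| ACT+MBRP only, OR 2.7, 40%/20% | 0.33 | 0.30 | 0.25 |
| Opposite directions by arm, OR 2.7, 20%/20% | 0.34 | 0.31 | 0.25 |
| Worst fifth of ACT+MBRP lost, standard care random | 0.34 | 0.31 | 0.25 |

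With mediator correlation 0.5 the middle column is about 0.25 throughout. The reason is specific to that value: it leaves almost no Week 13 to Week 37 association after baseline and mediator (0.43 − 0.43² − 0.5² = −0.005).

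**5. The mediated effect.** In the last scenario it is 0.146 against a true 0.151 at correlation 0.3, and 0.252 against 0.252 at 0.5.

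**The case against.** The strongest reply is that a regression of the 6-month outcome on treatment and baseline is not what 9.1 plans. The plan estimates a mediated effect by product of coefficients, with weekly mechanism measures in the likelihood. This stands in large part: the mediated effect is almost unbiased even in a near-worst case, and the mediators reduce the bias in the total effect. They remove it only if they account for nearly all of the link between the two visits, which the plan cannot assume.

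A second reply is that section 9.6 points to both 9.1 and 9.2 for analysis details, so the mixed model may be intended. That is possible, but 9.2 gives no outcome, visit term, covariate or contrast for it.

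A third is that the covariate rule already deals with missingness. For baseline variables it helps. For Week 13 outcomes it causes the loss shown in step 3.

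Two stronger readings are tempting. A reader might infer that drop-out will bias the effect, by a third or so. The documents do not support that. Bias needs loss that depends on Week 13 response beyond what the model holds, and that differs by arm in rate or mechanism. A one-third excess needs extreme dependence or opposed mechanisms. The plan raises differential attrition only as something to check. A reader might also infer that N = 120 is a miscalculation. It reproduces as a group-by-time test, and 9.2 supports 120 separately through mediation power.

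**Conclusion.** The mismatch holds: the treatment-effect model assumed in 9.2 is missing from 9.1, and Week 13 clinical outcomes have no stated role there.

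Three consequences follow, of unequal certainty.
- At the plan's own d and correlation, the 6-month baseline-adjusted comparison has about 33% power at 60 per arm, not 80%. This does not depend on drop-out.
- If the covariate rule is applied to Week 13 outcomes, about 30% of the effect is absorbed (0.25 becomes 0.175).
- If loss depends on Week 13 response and differs by arm, the total effect at 6 months is moderately overstated: 0.28 to 0.29 (12% to 16%) under moderate dependence and up to about 0.34 (36%) near the worst case. The excess is smaller with the mediators in the likelihood, and nil if loss is random or the same in both arms.

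The mediated effect is little affected. The bias figures rest on assumed loss patterns and on equal correlation across visits. The primary aim is descriptive feasibility, so this concerns Aim 2 only.

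**What to change.** In section 9.1:
- Specify the treatment-effect model: Week 13 and Week 37 outcomes modelled jointly by maximum likelihood, baseline as covariate, treatment-by-visit terms, and the Week 37 contrast reported.
- In the latent growth mediation models, include the Week 13 clinical outcome as an auxiliary variable, correlated with the other variables but not a predictor of the 6-month outcome.
- Limit the covariate rule to baseline variables. Enter post-randomisation variables related to missingness as auxiliaries.

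In section 9.2, say which contrast the 80% refers to. The joint model does not restore 80% power at Week 37: with complete data its Week 37 contrast is the baseline-adjusted comparison of step 2, at about 33%.

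The cost is wording only. The data are already scheduled, and the joint model recovered about 0.25 in every scenario run.
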